NOTE A: The extension in the week 72 visit for US participants applies only to study participants with completed week 24/SVR visit by the date of the A5360 Version 1.0 Clarification Memo #3, dated 04/09/20.

NOTE B: The extension in the week 72 visit also covers **US** participants who time out of the week 72 window (implemented via CM #3, dated 04/09/20), before the approval of A5360 Version 1.0 LOA #4, dated 06/22/20.

NOTE C: If the week 72 in-person visit for US participants cannot be completed by October 31, 2020, this will be considered a missed visit.

NOTE D: The extension in the week 72 visit also covers non-US participants who time out of the week 72 window before the approval of A5360 Version 1.0 LOA #5, dated 07/28/20.

NOTE E: If the week 72 in-person visit for non-US participants cannot be completed by February 28, 2021, this will be considered a missed visit.

2. Section 6.2.4, Post-Entry Evaluations, the following subsection has been added:

Alternate Completion of Post-Entry Evaluations

- Post-SVR week 48 visit:
 - 1) For non-US participants: The post-SVR week 48 in-person visit may be scheduled to occur up to and including 56 days after the week 48 ideal visit date. Complete the week 48 visit per Table 6.1-2 (Schedule of Evaluations: Step 2 - Visits Post SVR Evaluation).
 - 2) For all participants: If a week 48 in-person visit cannot be completed before the visit window closes, enter the visit as, "Participant unable to come to clinic due to COVID-19," using the instructions provided by the Data Management Center (DMC), entitled, "COVID-19 DMC Updates-FINAL."
- Post-SVR week 72 visit:
 - 1) For US participants: The post-SVR week 72 in-person visit may be scheduled through October 31, 2020. Complete the week 72 visit per Table 6.1-2 (Schedule of Evaluations: Step 2 - Visits Post SVR Evaluation).

NOTE: If a week 72 in-person visit cannot be completed for a US participant by October 31, 2020, this will be considered a missed visit.

- 2) For non-US participants: ~~If a week 72 in person visit cannot be completed before the visit window closes, contact the A5360 core team ([contact]) for further guidance. The post-SVR week 72 in-person visit may be scheduled through February 28, 2021. Complete the week 72 visit per Table 6.1-2 (Schedule of Evaluations: Step 2 - Visits Post SVR Evaluation).~~

NOTE: If a week 72 in-person visit cannot be completed for a non-US participant by February 28, 2021, this will be considered a missed visit.

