The following information affects the A5360 study and must be forwarded to each site's institutional review board (IRB)/ethics committee (EC) as soon as possible for their information and review. This Letter of Amendment (LOA) must be approved by the IRB/EC before implementation.

The following information may also affect the Sample Informed Consent. The IRB/EC is responsible for determining the process of informing participants of the contents of this LOA.

Upon receiving final IRB/EC and any other applicable regulatory entity approvals for this LOA, sites should implement the LOA immediately. Sites are still required to submit an LOA registration packet to the DAIDS Protocol Registration Office (PRO) at the Regulatory Support Center. Sites will receive a registration notification for the LOA once the DAIDS PRO verifies that all required LOA registration documents have been received

and are complete. An LOA registration notification from the DAIDS PRO is not required prior to implementing the LOA. A copy of the LOA registration notification, along with this letter and any IRB/EC correspondence, should be retained in the site's regulatory file.

The main reason for this LOA is to provide guidance for the resumption of study visits in follow-up to the COVID-19-related Clarification Memo #3 (CM #3), dated 04/09/20, as US and Non-US sites begin to open to research visits. This LOA is formal notification that the temporary pause of all study visits as stated in CM #3 is now lifted. All sites should contact study participants when sites are able to resume in-person research visits to schedule the participant's next visit. This contact can be considered the remote contact corresponding to week 42 or week 68 and must be documented in the participant's study file.

This LOA is being implemented for the following reasons:

- A team decision has been made to extend the upper window for the week 72 in-person visit for US sites, to October 31, 2020, which is the last date for which this visit can be completed. If US sites are unable to complete the week 72 in-person visit by this date, this will be considered a missed visit. In response, the following sections have been updated: Table 6.1-2, section 6.2.4, and section 6.2.5.
- Per DAIDS directive, COVID-19-related changes made via CM #3 have been incorporated. In response, the following sections have been updated: Table 6.1-2, section 6.2.4, and section 6.2.5.

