10.2.3 Other Outcome Measures

- 10.2.3.1 HCV reinfection defined as detectable HCV RNA and HCV sequence from subsequent to evaluation of SVR response, distinct from the baseline sequence and defined only among SVR responders
- 10.2.3.2 Change in FIB-4 between study entry and final study evaluation, defined only among SVR responders
- 10.2.3.3 Treatment emergent RASs among SVR non-responders
- 10.2.3.4 Quality of life (health related utility) before and after HCV cure
- 10.2.3.5 Cost per SVR attained- both globally and stratified by country - calculated using country-specific costs and expressed in US\$ 2017.
- 10.2.3.6 Mode of remote participant contact over time

10.2.3.7 Number and timing of unplanned visits, number of types of evaluations at unplanned visits

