12.3 General Approach to Costing

The cost/SVR attained will be assessed from two perspectives.

12.3.1 The perspective of the clinic/program/site treating the participant (program perspective). These costs include the cost of staff, laboratory monitoring, and medications involved in delivering HCV treatment to a participant. These costs begin at week 0 and continue through the week 24/SVR evaluation. The program cost perspective is helpful to those who administer a clinic or treatment program who want to understand how MINMON would impact their program budget.

There are two cost components from the program perspective:

1. Cost of HCV medications
2. Cost of planned and unplanned study visit evaluations between week 0 and the week 24/SVR evaluation visit

12.3.2 The healthcare sector perspective—the health sector perspective is broader than the program perspective. It includes the costs of staff, laboratory monitoring and medications between weeks 0 and 24, the cost of healthcare

utilization outside of the study site between weeks 0 and 24, and any changes in utilization that may occur in the future as the result of the participant attaining SVR.

There are four cost components from the healthcare sector perspective:

1. Cost of HCV medications
2. Cost of planned and unplanned study visit evaluations between week 0 and the week 24/SVR evaluation visit
3. Cost of healthcare utilization outside of study sites between week 0 and the week 24/SVR evaluation visit
4. Cost saving (or additional cost) that may accrue because a person attains SVR and subsequently uses fewer (or more) healthcare resources. This cost saving (cost) is defined as the DIFFERENCE in healthcare utilization per month measured at the week 48 visit compared to the week 0 visit. The healthcare utilization questionnaire measures utilization over a 4-week recall period. This is defined as healthcare utilization per month. The difference in healthcare utilization per month between the week 48 assessment and the week 0 assessment is the monthly savings (or cost) attributable to attaining SVR. It will be assumed that the monthly savings (cost) applies to every month between week 24 and week 72.

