In addition, because this estimate of cost savings is uncertain, sensitivity analyses will be used to explore different estimates of saving attained including: 1) difference in utilization measured at the week 72 visit and the week 0 visit, 2) difference in utilization measured at week 72 and week 48 visits. In both of these sensitivity analyses, it will be assumed that the monthly savings (or cost) we estimate applies to every month between weeks 24 and 72.

Measures of utilization will be translated to cost (expressed in currency rather than units of resources consumed) using WHO CHOICE country-specific unit costs (http://www.who.int/choice/cost-effectiveness/inputs/health_service/en/).

It will be assumed that all resource utilization between weeks 0 and 24 is related to HCV medications. As a result, the cost estimate will tend to be biased toward a higher cost/SVR attained.

The primary analysis will be conducted in an intention to treat framework, whereby participants who are LTFU and do not return for the week 24/SVR evaluation visit are assumed to be treatment failures and not counted as "SVR" in the cost/SVR attained calculation. This approach will also tend to bias results to a higher cost/SVR attained. A sensitivity analysis will explore cost/SVR when it is assumed that the rate of SVR among those lost to follow-up at week 24 is similar to the SVR rate among those with week 24 confirmation of cure.

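### The healthcare-sector costing credits the whole week 48 minus week 0 change in utilization to cure, although some week 48 and more week 72 visits fall after the March 2020 visit pause and all relevant week 0 visits fall before it

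*Protocol*

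**What the plan says.** Protocol 12.3.2 lists four cost components for the healthcare sector perspective. The fourth, the saving or extra cost that follows cure, is "defined as the DIFFERENCE in healthcare utilization per month measured at the week 48 visit compared to the week 0 visit". The protocol states that this difference "is the monthly savings (or cost) attributable to attaining SVR", and then: "It will be assumed that the monthly savings (cost) applies to every month between week 24 and week 72". Utilization is self-reported over the past 4 weeks (6.3.15).

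Protocol 12.3 calls the estimate uncertain and names two sensitivity analyses: "difference in utilization measured at the week 72 visit and the week 0 visit" and "difference in utilization measured at week 72 and week 48 visits". Both are extrapolated over the same weeks 24-72. Cost per SVR is reported overall and by country (12.2.1).

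Clarification Memo #3 (9 April 2020) refers to a pause memo of 23 March 2020. Letter of Amendment #4 (22 June 2020) is the "formal notification that the temporary pause of all study visits as stated in CM #3 is now lifted". Outside the US the window was widened: "The post-SVR week 48 in-person visit may be scheduled to occur up to and including 56 days after the week 48 ideal visit date"; the US week 48 window stayed at ±28 days. Week 72 could be completed until 31 October 2020 (US) and 28 February 2021 (non-US). Letters #4 and #5 name only Table 6.1-2 and sections 6.2.4 and 6.2.5 as updated.

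**The concern.** Component 4 is an uncontrolled before-after difference. It measures the effect of cure only if nothing else changed use of clinics, emergency departments and hospitals between the two visits. The study's own letters show that the setting did change, and section 12 was not revisited. If access to care fell, the fall would be booked as a saving from SVR and multiplied over twelve 4-week periods. That would lower cost per SVR, whereas both biases that 12.3 acknowledges (charging all week 0-24 utilization to HCV medication, and counting participants lost to follow-up as failures) raise it. Higher utilization would do the reverse. Because windows and deadlines differ between US and non-US sites, exposure can differ by country in a result that is reported by country.

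**Working it through.** **Inputs.** Pause 23 March 2020 (Clarification Memo #3), lifted 22 June 2020 (Letter #4). Week 48 = entry + 336 days; week 72 = entry + 504 days. Non-US week 48 window +56 days; last week 72 dates as above (Letter #5). Protocol in the field on 14 February 2018 (template changes listed in an earlier letter of amendment). Planned accrual from Protocol 10.4.

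**The plan's own figures.** Uniform accrual: 400/25 = 16 months. Slower accrual: 12 + (400 - 60 - 90)/20 = 24.5 months, against about 24 stated. Both reproduce.

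**Cut dates.**
- Nominal week 48 on or after the pause: entry from 23 March 2020 - 336 days = 22 April 2019.
- Nominal week 72 on or after the pause: entry from 23 March 2020 - 504 days = 5 November 2018.
- Latest entry compatible with a permitted week 72 visit: 28 February 2021 + 28 - 504 days = 10 November 2019. Week 0 therefore precedes the pause for all such participants.
- Non-US week 48 window still open when the pause was lifted: entry from 22 June 2020 - 392 days = 27 May 2019.

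**Share of participants.** Entry dates are not in the documents, so accrual is assumed uniform. Share = (accrual end - cut date)/(accrual length). The first row is the planned 25 per month from the field date. The other start and end dates are assumptions; 13 October 2019 is the last entry with a nominal week 72 by 28 February 2021.

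| Assumed accrual | Days | Nominal week 48 after pause began | Nominal week 72 after pause began | Week 48 window open on 22 June 2020 if +56 days everywhere |
|---|---|---|---|---|
| 14 Feb 2018 to 16 Jun 2019 | 487 | 55/487 = 11% | 223/487 = 46% | 20/487 = 4% |
| 1 Jul 2018 to 30 Jun 2019 | 364 | 69/364 = 19% | 237/364 = 65% | 34/364 = 9% |
| 1 Jul 2018 to 13 Oct 2019 | 469 | 174/469 = 37% | 342/469 = 73% | 139/469 = 30% |
| 1 Jan 2019 to 13 Oct 2019 | 285 | 174/285 = 61% | 100% | 139/285 = 49% |

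The last column is the relevant one for the base case: a week 48 visit whose window closed during the pause is missing, not contaminated. Missing visits also leave the denominator. As a share of week 48 visits that could take place, the last column becomes 4/(89 + 4) = 4% in the first row and 49/(39 + 49) = 56% in the last.

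**Sensitivity analyses.** The week 72 share exceeds the week 48 share in every row, so week 72 minus week 0 is more exposed than the base case. In week 72 minus week 48, the share of participants with at least one questionnaire after the pause began is again the week 72 share. Where both visits fall after it, the effects may partly cancel. Neither contrast is free of the problem.

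**Size if cure had no effect.** Suppose utilization after the pause began differed from baseline by an assumed 10% to 50%. The rule would then credit cure with share × change of baseline monthly utilization. At week 48, using 4% to 56%, this runs from 0.04 × 10% = 0.4% to 0.56 × 50% = 28%. Over twelve periods that is about 0.05 to 3.4 baseline 4-week periods of care.

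**The case against.** The strongest reply is that the analysis plan for cost is not in view. Cost per cure is an exploratory objective (1.4.5), and SAP 2.1 defers analyses outside the primary manuscript to a Secondary SAP, which may deal with calendar period. Protocol 12.3 also introduces its sensitivity analyses with an open list. This stands as a limit: the gap is shown for section 12, the COVID-era letters and the primary SAP only.

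Second, many nominal post-pause week 48 visits never happened. If the last US entry is the one whose nominal week 72 falls on 31 October 2020 (15 June 2019), the last US week 48 window closes on 13 June 2020, before the pause was lifted. Allowing the -28 day window at week 72 moves this to 11 July 2020, so US exposure at week 48 is nil or small. The -28 day window at week 48 also let some visits take place before the pause. This stands, and is why the nominal 11-61% should not be read as contamination.

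Third, the documents give no size or direction for a pandemic effect. That stands too.

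A reader might also infer that quality of life is affected in the same way. The documents do not support that. The outcome is "Quality of life (health related utility) before and after HCV cure", with no time point named. EQ-5D is also collected at week 24/SVR, which falls almost wholly before the pause in these scenarios (0-2%), and neither 10.6 nor the primary SAP specifies a week 48 or 72 comparison with week 0.

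**Conclusion.** The point holds for healthcare utilization only. Followed as written, component 4 mixes calendar-period change with the effect of cure and labels the sum as due to SVR, and the planned sensitivity analyses would not reveal this. Exposure of the base case is partial: at most 4-49% of week 48 windows were still open when the pause was lifted, under assumed uniform accrual and the longest window for all sites. Nominal week 72 exposure is 46-100%. These ranges rest on assumed entry dates, and 23 March 2020 is a study-operations date that need not match when care changed in each country.

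It would go too far to say that pandemic effects have been credited to cure, or that the saving is overstated: the direction is unknown. The issue reaches one of four components in one of two costing perspectives. The program perspective and the primary SVR and SAE analyses are untouched. It is worth correcting because the correction is cheap.

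**What to change.** In Protocol 12.3 and the Secondary SAP:

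- Flag each week 48 and week 72 utilization questionnaire by whether its 4-week recall period ended before 23 March 2020.
- Keep all visits as the base case. Add a sensitivity analysis of component 4 (week 48 minus week 0) restricted to pre-pause assessments, and report component 4 by period, overall and by country where numbers allow.
- Describe the pooled difference as a before-after change instead of attributing it to SVR, and add calendar period to the biases discussed in 12.3, noting that lower utilization would push cost per SVR down.

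The cost is wording and a date flag on data already collected. The pre-pause estimate will have fewer participants, mainly fewer late-enrolling non-US ones, and a wider interval, which is why it belongs as a sensitivity analysis and not as the base case.

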12.4 Resource Utilization Data Collection

12.4.1 Cost of HCV Medications

We will price HCV therapy by country based on the negotiated price with ministries of health. In the U.S., there is no single cost of HCV therapy. For U.S. sites, we will price SOF/VEL using the federal supply schedule. Because the cost of therapy is dynamic and changes by setting and time, we will use sensitivity analyses to explore the impact of drug prices on the cost-benefit of treatment.

12.4.2 Cost of Planned and Unplanned Study Visits

We will consider two components of the cost of a study visit: a) cost of provider time, and b) cost of labs and assessments. Cost of the healthcare visits (Doctor/physician and staff time)—we will use WHO CHOICE estimates of outpatient care delivery costs by country. We will include the week 0 visit (not the screening visit as it is a study procedure with no real-world analogue) and the visit for week 24/SVR evaluation. In addition, we will include any unplanned visits between week 0 and the week 24/SVR evaluation.

We will cost laboratory tests using the national fee schedule for public sector healthcare payers in each country. For example, we will use the Center for Medicare and Medicaid Services (CMS) reimbursement schedule for laboratory test costs in the U.S. and the National Health Laboratory Service schedule for sites in South Africa.

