Laboratory Specialist

[name], BS
ACTG Network Coordinating Center
Social & Scientific Systems, Inc.
Laboratory Science Group
[name]
[name]
[contact]
[contact]
Email: [contact]

DAIDS Clinical Representative

[name] [name], FACP
CCRB/TRP/DAIDS/NIAID/NIH/DHHS
Therapeutics Research Program
[name]
[name]
[contact]
[contact]
Email: [contact]

2. Section 6.3.4, Model for End-Stage Liver Disease (MELD) Score

The following note has been added after the first paragraph to read:

The MELD score measures the mortality risk in participants with end-stage liver disease. It is used as a disease severity index to help prioritize allocation of organs for transplant. In order to calculate the MELD score, total bilirubin (mg/dl), sodium (mEq/L), INR, and serum

creatinine (mg/dl) values are needed.

NOTE: The MELD score at entry should be calculated using the INR value from screening.

3. Section 6.3.8, Medical History

The first paragraph has been updated to read:

The medical history must include all signs and symptoms regardless of grade and all diagnoses identified by the ACTG criteria for clinical events and other diagnoses regardless of grade within 30 days prior to entry. In addition, the following diagnoses should be reported regardless of when the diagnosis was made:

- AIDS-defining conditions (only for HIV-1 co-infected participants)
- Bone fractures (verbal history accepted)
- Coronary heart disease
- Cancer (exclusive of basal/squamous cell skin cancer)
- Diabetes
- Tuberculosis
- Chronic HCV (If available, appropriate documentation from medical records of chronic HCV-infection, defined as having a documented HCV-positive antibody serology for greater than 6 months.)
- Chronic HBV
- Substance use (injection, non-injection drugs, and alcohol) captured via the WHO ASSIST instrument
- **HIV-1 diagnosis (for HIV-1 co-infected participants)**

Any allergies to any medications and their formulations must also be documented.

4. Section 6.3.10, Clinical Assessments

The third paragraph located after Targeted Physical Exam has been updated to read:

Post entry, record the following targeted events regardless of grade:

- ~~Uterine pregnancy~~
- AIDS-defining conditions (refer to the CDC HIV Classification and the WHO Staging System for HIV Infection and Disease)
- Tuberculosis
- Chronic HBV
- Ascites
- Hepatic encephalopathy
- **Variceal bleeding**

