If the monitoring protocol that is being proposed is found to be efficacious and comparable to what is currently being observed in clinical settings globally, it would imply that the HCV-infected persons, for the large part, could be treated from settings with minimal infrastructure. In fact, HCV care could be rolled out of primary health care centers where routine blood work is available—at baseline, one would need to perform a complete blood panel, hepatic function panel and a renal panel to stage liver disease. Point-of-care HCV antibody tests are already available. If the individual is a decompensated cirrhotic, he/she could be referred to a tertiary care center. If not, treatment could be initiated following HCV RNA quantification. The availability of the GeneXpert cartridges for quantification of HCV RNA [24] has the potential to transform any center with electricity and an individual with high-school level of education to perform HCV RNA quantification. There are approximately four to five times the number of people living with HCV globally compared to HIV—to ensure that treatment reaches them all and to truly have a shot at eradication of HCV, it is critical to improve access while reducing cost and associated treatment complexities.

However, what is being proposed is novel but high-risk and has never been piloted for the delivery of HCV care. It is possible that adherence and treatment completion rates, if the entire treatment supply is provided upfront with no health care contact thereafter for the remainder of the treatment duration, could be inferior to the SOC. This single-arm study, open to US and non-US sites, will enroll 400 participants, all of whom will be followed using the MINMON protocol only. The rationale for limiting enrollment of HIV-coinfected participants to <50% is to ensure the findings of this trial are generalizable to all HCV infected persons. Given that this trial will be recruiting from ACTG sites that are primarily HIV clinics, it is highly possible that there may be an overrepresentation of HIV-infected persons.

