3.0 STUDY DESIGN

This study will enroll 400 participants who will be followed using a MINMON protocol for a duration of 24 weeks in order to obtain primary outcome information regarding SVR status, as well as additional information for secondary objectives over the longer duration of 72 weeks. The MINMON strategy is comprised of: 1) minimal pre-treatment assessment including confirmation of viremia by HCV RNA and liver disease staging using routine clinical exam and non-invasive parameters (ALT, AST, and platelet count [and bilirubin, albumin, and INR in persons with evidence of cirrhosis by FIB-4]) and no genotyping; 2) distribution of complete HCV treatment course at study initiation (i.e., 84 days of SOF/VEL); 3) no planned on-treatment laboratory monitoring; 4) no planned clinic or pharmacy visits prior to SVR evaluation; and 5) remote contact at treatment week 4 and post-treatment at week 22 to update locator information and to facilitate attendance at the SVR evaluation visit (weeks 22 to 28). The week 4 remote contact will include adherence assessment and reinforcement which is also considered to be a part of the MINMON strategy.

All participants will be treatment-naïve, with active HCV-infection, with or without HIV-1 co-infection, and if cirrhotic, will be classified as compensated cirrhotics based on CTP score. All participants will receive study-provided treatment (FDC of SOF/VEL) for a duration of 12 weeks followed by evaluation 12 weeks later to ascertain SVR status. Upon SVR evaluation, all participants will enter Step 2 of the study and will be followed for an additional 48 weeks to examine liver disease regression post-SVR, measure the incidence of HCV re-infection, and other non-primary outcomes. Measures of disease regression after cure are important to understanding future disease burden and cost associated with liver disease. Reinfection rates are critically important for both public health planning and advocacy purposes when seeking to expand the availability of HCV treatments. In addition, cost-benefit analyses will be conducted using cost data and outcomes gathered from this study.

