6.0 CLINICAL AND LABORATORY EVALUATIONS

6.1 Schedule of Evaluations

6.1-1: Schedule of Evaluations: Step 1- Visits up Until SVR Evaluation

Evaluation	Screening	Entry/Week 0	Weeks			SVR Evaluation Visit (if week 24 visit is missed; can occur up to week 72)	Unplanned Study Visits (see section 6.2.6)
			4	22	24		
			Window \pm 7 days		Window -14/+28 days		
Documentation of Active HCV Infection	X						
Documentation of HIV-1 Status	X						
Calculated FIB-4 Score	X				X	X	As needed.
MELD Score		X					
Documentation of Cirrhosis Status	X				X	X	As needed.
Calculated CTP Score (if cirrhotic by FIB-4)	X				X	X	
Liver Elastography (see section 6.3.7)		X			X	X	
Medical History	X	X					
Medication History	X	X					
Clinical Assessments	X	X			X	X	As needed.
Hematology	X	X			X	X	
Liver Function Tests	X	X			X	X	
Blood Chemistries	X	X			X	X	As needed.

Evaluation	Screening	Entry/Week 0	Weeks			SVR Evaluation Visit (if week 24 visit is missed; can occur up to week 72)	Unplanned Study Visits (see section 6.2.6)
			4	22	24		
			Window \pm 7 days		Window -14/+28 days		
Calculated Creatinine Clearance	X						
INR	X				X	X	As needed.
Pregnancy Testing	X	X			If pregnancy is suspected.		
HBV Panel	X						
CD4+ (if HIV+)	X				X	X	
Plasma HIV-1 RNA (if HIV+)	X				X	X	
Plasma HCV RNA	X				X	X	
Stored Plasma/PBMC/Serum		X			X	X	As needed. (Plasma sample will be stored if blood sample obtained.)
Adherence Assessment			X (via remote contact)		X	X	
Health Outcomes Questionnaire		X			X	X	X
Health Care Utilization Questionnaire		X			X	X	X
Substance Use Questionnaire		X			X	X	

Evaluation	Screening	Entry/Week 0	Weeks			SVR Evaluation Visit (if week 24 visit is missed; can occur up to week 72)	Unplanned Study Visits (see section 6.2.6)
			4	22	24		
			Window \pm 7 days		Window -14/+28 days		
HCV Therapy Dispensed/First Dose Observed		X					
Adherence Education and Counseling		X					
Pregnancy Prevention Counseling	X	X					
Cirrhosis Counseling		X			X	X	
HCV Risk-reduction Counseling		X			X	X	
Locator Information		X	Update information, if needed.				
Remote Contact with Participants Outside of Planned Clinic Visits			X	X (see note in section 6.2.4)			

6.1-2: Schedule of Evaluations: Step 2- Visits Post SVR Evaluation

Evaluation	Weeks			
	42	48	68	72
	Window +28 days			
Calculated FIB-4 Score		X		X
MELD Score		X		X
Calculated CTP Score (if cirrhotic by FIB-4)		X		X
Liver Elastography (see section 6.3.7)		X		X
Clinical Assessments		X		X
Hematology		X		X
Liver Function Tests		X		X

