12.6 Estimation of Cost/SVR Outcome

- 12.6.1 Program perspective. We will estimate the mean cost per participant including:
 - Cost of medications
 - Cost of all planned and unplanned study visits between weeks 0 and 24/SVR evaluation including staff time and laboratory tests

- 12.6.2 Healthcare sector perspective
 - Cost of medications
 - Cost of all planned and unplanned study visits between weeks 0 and 24/SVR evaluation including staff time and laboratory tests
 - Cost of healthcare utilization between weeks 0 and 24/SVR evaluation
 - The DIFFERENCE in healthcare utilization as measured at weeks 0 and 48

Cost/SVR attained in each country will be calculated, as well as for the entire study population. Cost/SVR both in local currency and in international dollars will be stated. The cost/participant who does NOT attain SVR will also be estimated. Sensitivity analyses will demonstrate the impact of HCV therapy costs on the cost-benefit of MINMON.

In addition, although there is no control arm to which we can compare the cost/SVR attained in MINMON, we will estimate the cost/SVR attained for the standard of care treatment protocol based on the cost of laboratory tests and medications and the planned schedule of events for a standard of care treatment course.

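### As written, cost per SVR leaves out MINMON's own pre-treatment HCV RNA test (and INR in FIB-4 cirrhotics), because costing starts at week 0 and these tests are scheduled only at screening

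*Protocol*

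**What the plan says.** **Costing window.** Section 12.4.2 names the planned visits to be costed: "We will include the week 0 visit (not the screening visit as it is a study procedure with no real-world analogue"), and then the week 24/SVR visit; unplanned visits in between are added. For the program perspective, section 12.3.1 states: "These costs begin at week 0 and continue through the week 24/SVR evaluation". Section 12.6 places laboratory tests in the same window for both perspectives: "Cost of all planned and unplanned study visits between weeks 0 and 24/SVR evaluation including staff time and laboratory tests".

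**Schedule.** Table 6.1-1 ("Schedule of Evaluations: Step 1- Visits up Until SVR Evaluation") marks plasma HCV RNA and INR at screening and again at week 24/SVR; the entry column is blank for both. The version of the table in Clarification Memo #2 is the same on this. A Letter of Amendment note to section 6.3.4 confirms it for INR: "The MELD score at entry should be calculated using the INR value from screening".

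**Strategy.** Section 3.0 lists as the first component of MINMON a "minimal pre-treatment assessment including confirmation of viremia by HCV RNA and liver disease staging using routine clinical exam and non-invasive parameters", with ALT, AST and platelets for all "and bilirubin, albumin, and INR in persons with evidence of cirrhosis by FIB-4". In the roll-out described in section 2.2, for people who are not decompensated, "treatment could be initiated following HCV RNA quantification".

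**Savings after cure.** Section 12.3.2 takes the week 48 versus week 0 difference in utilization as the saving due to SVR. Section 12.3 adds two sensitivity analyses: week 72 versus week 0, and week 72 versus week 48.

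**The concern.** The reason given for leaving out screening may fit the extra trial visit. It does not fit the HCV RNA test done there. Section 2.1 describes HCV RNA before treatment in routine care in Brazil, India and Thailand, and Table 2.1-2 marks a baseline HCV RNA for those three countries and the US. A visit exclusion therefore also removes a test that the strategy itself requires.

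Cost per person cured is a stated objective (1.4.5), and section 12.6 sets it beside a modelled standard-of-care figure. Section 12.3 tells the reader of two biases, both toward a higher cost per SVR: all utilization in weeks 0 to 24 is attributed to HCV medication, and participants lost to follow-up count as failures. The omitted tests act the other way and are not mentioned.

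The week 72 minus week 48 analysis raises a separate problem. It is offered as an alternative estimate of the saving from SVR, yet both visits fall after SVR evaluation.

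**Working it through.** The documents give no cost per SVR and no unit prices, so there is no figure to reproduce. The check sets the schedule against the costing window and counts tests.

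**1. Which pre-treatment tests are costed?** (Table 6.1-1, sections 3.0 and 6.3.11)

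| Strategy test before treatment | Screening | Entry | Costed? |
|---|---|---|---|
| ALT, AST (liver tests) | yes | yes | yes, at entry |
| Platelets (hematology) | yes | yes | yes, at entry |
| Bilirubin, albumin (liver tests) | yes | yes | yes, at entry |
| HCV RNA | yes | no | no |
| INR (FIB-4 cirrhotics) | yes | no | no |

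Only HCV RNA and INR fall out. The strategy uses two HCV RNA tests per participant who attends for SVR (pre-treatment and SVR); the plan costs one.

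**2. Size per participant.** HCV RNA: up to 1. INR: at most the cirrhosis cap over the sample size (section 10.3), 80/400 = 0.20.

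**3. Size per SVR.** With mean cost per participant divided by the SVR proportion s, the omitted amount is (c_RNA + 0.20 × c_INR)/s at most, where c is a unit price. For s, assume 93% to 97%, the middle range in section 2.2.

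- HCV RNA: 1/0.97 = 1.03; 1/0.93 = 1.08 tests per SVR.
- INR: 0.20/0.97 = 0.21; 0.20/0.93 = 0.22 tests per SVR, at most.
- Over a wider assumed range of 98% to 90%: 1.02 to 1.11 HCV RNA and at most 0.20 to 0.22 INR. The result depends little on s.

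**4. Other side of the ledger.** At week 24/SVR, Table 6.1-1 schedules INR without limiting it to cirrhotics, plus hematology, liver tests, chemistries, elastography where available and, if HIV-positive, CD4+ and HIV-1 RNA. Section 3.0 names none of these as strategy components after treatment. If all are costed, INR alone adds one per attendee, against at most 0.20 omitted before treatment.

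**5. Week 72 minus week 48.** Let U0, U48 and U72 be utilization per 4 weeks. The saving is applied to (72 − 24)/4 = 12 four-week periods.

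- Main analysis: 12 × (U0 − U48).
- First sensitivity analysis: 12 × (U0 − U72).
- Second sensitivity analysis: 12 × (U48 − U72).

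If utilization falls after cure and stays down, U48 = U72 < U0. The first two expressions are then equal and positive, and the third is zero however large the fall. U0 does not enter it.

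**The case against.** **Where to start the costing is a choice.** Section 12.3.1 costs the delivery of treatment and declares week 0 as the start; confirming viremia can be seen as upstream of that. Sections 4.1.3 and 6.3.13 also allow for an HCV RNA result obtained before the screening visit. This stands in part: one omitted test per participant is an upper bound, and the figure is lower if a routine-care result is judged outside program cost. But the plan does not argue from a boundary. It says that screening has no counterpart in practice, which sections 2.2 and 3.0 contradict for this test.

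**The lists in section 12 are not complete.** Section 2.2 promises to cost remote contacts and the SVR-visit incentive, which section 12 does not list, so tests might be added in the same way. That is fair as to silence, but here the screening visit is excluded expressly.

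**The exclusion concerns provider time only.** Section 12.6 closes this route, since it puts laboratory tests in the same window.

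**Materiality.** Prices are absent, the objective is exploratory and outside the primary SAP, and drug-price sensitivity analyses are already planned (12.4.1). The amount may be small next to drug cost. This stands.

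**Stronger readings that the documents do not support.** A reader might infer that cost per SVR is biased downward overall; the extra week 24/SVR labs in step 4 prevent that conclusion. A reader might also infer that the standard-of-care comparison is off by one test. Section 12.6 does not say which schedule or baseline tests that estimate uses, and if shared tests are left out on both sides, the difference in cost per participant is unaffected and only the absolute figures are too low. Finally, one might charge tests in people never treated, using the share under 20% that section 2.2 gives for decompensated cirrhosis and HBsAg positivity. The roll-out in that section refers decompensated patients before HCV RNA quantification, so this share does not count tests used.

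**Conclusion.** The inconsistency is real and limited. Taken literally, section 12 yields a cost per SVR without one of the strategy's own tests: up to 1 HCV RNA per participant (1.03 to 1.08 per SVR at an assumed SVR of 93% to 97%) and at most 0.20 INR per participant. The upper figures assume that every pre-treatment HCV RNA test is chargeable and that the cirrhosis cap is filled. The omission acts downward, opposite to the two biases that section 12.3 names. The net direction of laboratory cost is not established, and the monetary size is unknown.

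The week 72 minus week 48 analysis cannot estimate savings from attaining SVR, whatever the data show. It is one of two sensitivity analyses and affects the healthcare-sector perspective only.

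Both points are worth correcting before the cost analysis is run. Neither touches the SVR or SAE analyses.

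**What to change.** - In 12.3, 12.4.2 and 12.6, keep the trial-only screening visit excluded, but add a flat charge per participant for one pre-treatment HCV RNA test, and for INR when FIB-4 is 3.25 or higher, as if done at week 0. Do not add labs already repeated at entry.
- State for each perspective whether a routine-care HCV RNA result used for entry is charged. A flat charge avoids having to separate the two sources; section 6.3.1 says that HCV documentation is not recorded on the eCRF.
- Give the standard-of-care estimate in 12.6 the same start point and the same shared baseline tests, with genotyping on that side only.
- If any part of the omission remains, name it and its direction among the biases in 12.3.
- Drop the week 72 minus week 48 analysis, or relabel it as a description of change after SVR evaluation.

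The cost is wording in section 12 and unit prices from the fee schedules already planned; no new data are needed. The downside is that MINMON's cost per SVR rises slightly.
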